Title: Comparison of 3 versus 6-Month Use of Professional Continuous Glucose Monitoring in the Treatment of Poorly Controlled, Non-Insulin Using T2DM Patients in a Primary Care Setting

NCT#: NCT03067480

Date: December 4th 2018

Research Abstract Proposal

Comparison of 3 versus 6-Month Use of Professional Continuous Glucose Monitoring in the Treatment of Poorly Controlled, Non-Insulin Using T2DM Patients in a Primary Care Setting

Primary Objective:

1. To determine whether 3-month versus 6-month professional CGM utilization improves time spent in target range of 70-140mg/dl in patients with poorly controlled T2DM not treated with insulin.

Secondary Objectives:

1. To determine whether 3-month versus 6-month professional CGM utilization improves hemoglobin A1c in patients with T2DM not treated with insulin.
2. To determine whether 3-month versus 6-month professional CGM utilization leads to more treatment intensification.

Background

For prescribers, the hemoglobin A1c (HbA1c) lab value is the most common monitoring used in primary care to assess diabetes control and determine if pharmacotherapy modification is warranted. For patients with type 2 diabetes (T2DM), self-monitoring blood glucose (SMBG) results may be performed to evaluate diabetes control, but these results must be communicated to the clinician in an effective and timely manner for the data to be useful in creating a patient-centered plan.¹ Structured SMBG plans that include a 7-point glucose profile over 3 days (fasting, pre and 2-hour post-meal, and bedtime) has demonstrated improved glycemic control in poorly controlled T2DM patients (HbA1c \geq 7.5%) not treated with insulin.² In this study, prescribers were more likely to make treatment changes when structured SMBG occurred compare to no structured SMBG. However, structured SMBG protocols are rarely implemented in primary care offices. Overall, the usefulness and cost-effectiveness of SMBG in T2DM patients treated with non-insulin therapies is conflicting and the American Diabetes Association (ADA) has assigned it an evidence-based grade of “E” for expert opinion.^{1,3} Professional continuous glucose monitoring (CGM) could represent another opportunity for prescribers to assess glycemic control over a 3-day period.

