Professional CGM measures interstitial glucose every 5 minutes via a glucose-oxidase-impregnated membrane during a 3–5 day period.⁴ The patient wearing professional CGM is blinded to the repeated measurements and the data is stored for retrospective analysis. The durable equipment used to perform professional CGM is owned and maintained by the practice site or clinician and can be used regularly with a variety of patients. Currently, insurance companies often determine the use of professional CGM in T2DM and frequency of use is variable. There is no data available comparing glycemic control in non-insulin treated patients with T2DM when professional

CGM is utilized at different frequencies or examining the best use of professional CGM in this subset of patients. This population represents a significantly large number of patients who are typically treated in primary care settings without an endocrinologist. The results of this trial could assist Medtronic in marketing professional CGM products to primary care providers.

Given the usefulness of the glycemic data provided by professional CGM, I hypothesize that patients who wear the professional CGM at 3-month intervals when spend more time in target range than those wear it at 6-month intervals. This hypothesis will be addressed in the following specific aims:

Specific Aims:

1. To determine the percent time spent in target range of 70-140mg/dl in poorly controlled patients with T2DM not treated with insulin.

Patients not receiving any insulin treatment with an HbA1c $\geq 7.5\%$ before their scheduled primary care appointment will be invited to participate in the study and wear professional CGM for at least 3 days at either 3 intervals (baseline, 3-month and 6-month) or 2 intervals (baseline and 6-month). After removal, the downloaded report will provide quantitative data to determine the percent of time spent in the target range. The 6-month data will be analyzed to determine if frequency of professional CGM wear positively affects time spent in target range.

2. To determine the hemoglobin A1c levels in poorly controlled patients with T2DM not treated with insulin.

Patients who consent to the study will have their HbA1c levels measured in our central lab at the clinic and recorded in the electronic medical record (EMR). This data is easily retrievable for reporting and would be analyzed to determine if frequency of professional CGM wear would positively affect HbA1c levels.

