3. To determine treatment modification in poorly controlled patients with T2DM not treated with insulin.

The EMR documents current and previous medication therapies including newly prescribed medications, increased or decreased dosage changes or termination of prescribed medication. Only FDA-approved medications for the treatment of type 2 diabetes will be monitored. The type of treatment modification and their frequencies can be retrieved from the EMR and analyzed to determine if frequency of professional CGM wear affects these outcomes.

Sample Size and Rationale

A calculated sample size of 20 patients will be needed to detect a 15% effect size (e.g., mean of 60% vs. 75% of time in target range) with a standard deviation of 10 and 90% power. Assuming a 25% drop out, planned enrollment is 25 patients with poorly

controlled T2DM (defined as last two consecutive HbA1c values between 7.5 – 10%) and who have not received insulin within the last 3 months.

Study Design

6-month, Prospective, Randomized, Single Center

Inclusion Criteria

- 18 years or older with a diagnosis of T2DM with a scheduled office visit with primary care provider within the next 4 weeks
- Last 2 HbA1c values between 7.5 – 10% measured in the last 12 months
- Treated with non-insulin therapies or therapeutic lifestyle changes
- Never worn professional CGM or have not worn in last 12 months
- Willing to perform requirements needed for professional CGM

Exclusion Criteria

- Current or previous treatment with any insulin within 3 months at baseline

Protocol or Study Plan

1. Identify patients via electronic medical record reporting based on inclusion criteria.
2. Contact and screen prospective participants either via phone call explaining the research project and objectives.
3. In patient expresses interest, complete the consent process and randomize participant into either 3-month or 6-month professional CGM.
4. **Baseline Visit**
 - a. Assign de-identified code to participate for confidentiality protection.
 - b. Measure demographic information, baseline HbA1c levels, baseline medication therapies and doses.
 - c. Place professional CGM placement and provide patient education for successful 3-day wear.
 - d. Schedule follow-up professional CGM placement visits at either
 - i. 3-month and 6-month or
 - ii. 6-month only.
 - e. Confirm scheduled primary care physician follow-up appointment(s).

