 - f. After patient returns CGM, download 3 color copies of CGM reports (one for physician, patient and research records)
 - g. Provide downloaded professional CGM reports to primary care physician prior to patient appointment for review. Inform physician a Certified Diabetes Educator (CDE) is available for consultation, as needed.
 - i. Contingency Plan – if in the event any reading are < 40mg/dl or > 400mg/dl, the physician will be contacted that same day through

the EMR system instead of waiting till the next scheduled appointment

5. 3-Month Visit

- a. if randomized to 3-month CGM arm
 - i. Confirm patient CGM placement visit approximately 1 week in advance.
 - ii. Place professional CGM placement and provide patient education for successful 3-day wear.
 - iii. Record any new HbA1c results and changes to medication therapies and/or doses.
 - iv. Confirm 6-month professional CGM placement visits.
 - v. Confirm scheduled primary care physician follow-up appointment(s).
 - vi. After patient returns CGM, download 3 color copies of CGM reports (one for physician, patient and research records)
 - vii. Provide downloaded professional CGM reports to primary care physician prior to patient appointment for review. Inform physician a Certified Diabetes Educator (CDE) is available for consultation, as needed.
 1. Contingency Plan – if in the event any reading are < 40mg/dl or > 400mg/dl, the physician will be contacted that same day through the EMR system instead of waiting till the next scheduled appointment
- b. If patient is NOT scheduled to receive CGM, then at 3 months:
 - i. Contact patient by telephone and ask to perform SMBG four times daily (before all meals and bedtime) for 3 days and bring the results to their scheduled physician visit

6. 6-Month Visit

- a. Confirm patient CGM placement visit approximately 1 week in advance.
- b. Place professional CGM placement and provide patient education for successful 3-day wear.
- c. Record any new HbA1c results and changes to medication therapies and/or doses.
- d. Confirm scheduled primary care physician follow-up appointment(s).
- e. After patient returns CGM, download 3 color copies of CGM reports (one for physician, patient and research records)
- f. Provide patient with \$50 gift card.
- g. Provide downloaded professional CGM reports to primary care physician prior to patient appointment for review. Inform physician a Certified Diabetes Educator (CDE) is available for consultation, as needed.

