 - i. Contingency Plan – if in the event any reading are < 40mg/dl or > 400mg/dl, the physician will be contacted that same day through the EMR system instead of waiting till the next scheduled appointment

7. Analyze and report data.

Schedule with key milestones

Fall 2016 – begin recruitment

Spring 2017 – all participants completed 3-month visit

Fall 2017 – all participants completed 6-month visit

Biostatistics and Data Analysis

Descriptive statistics including mean, standards deviation, frequency, etc. will provide the summary information for this study. A linear regression will be used to investigate if frequency of professional CGM wear (independent variable) positively affects time spent and HbA1C level (outcome variables) in target range. An appropriate transformation will be used if the normality is severely violated. Meanwhile, the significant changes of HbA1C overtime will be used to determine with a longitudinal data analysis. More specifically, repeated measure approach will be used for 3 intervals (baseline, 3-month and 6 month) and matched pair t-test will be used for 2 intervals (baseline and 6-month). Frequencies of in treatment modification would be analyzed using Chi-Square test. A $p < 0.05$ will be used to indicate statistically significant. All data analyses will be performed with SAS (version 9.4 Cary, NC, USA).

Start Date and End Date

October 1st 2016 – October 1st 2017 (approximate)

References

3. American Diabetes Association. Glycemic targets. Sec. 5. In Standards of Medical Care in Diabetes 2016. *Diabetes Care* 2016;39(Suppl. 1):S39–S46.
4. Blevins TC. Professional Continuous Glucose Monitoring in Clinical Practice 2010. *Journal of Diabetes Science and Technology.* 2010;4(2):440-456.

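### The only between-arm HbA1c analysis names no baseline HbA1c covariate, although baseline HbA1c is measured in both arms

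*Combined protocol and SAP*

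**What the plan says.** Secondary Objective 1 is a comparison of arms: "To determine whether 3-month versus 6-month professional CGM utilization improves hemoglobin A1c in patients with T2DM not treated with insulin".

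Biostatistics and Data Analysis meets it with one sentence: "A linear regression will be used to investigate if frequency of professional CGM wear (independent variable) positively affects time spent and HbA1C level". No covariate is named. The outcome is a level, with no time point given.

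The same section also tests HbA1c change over time, using repeated measures for three intervals and a paired t-test for two. Specific Aim 1 defines the three-interval and two-interval schedules as the two randomised arms.

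On data collection:

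- Specific Aim 2: "Patients who consent to the study will have their HbA1c levels measured in our central lab at the clinic".
- Baseline Visit, item 4b, common to both arms: "Measure demographic information, baseline HbA1c levels, baseline medication therapies and doses".
- 6-Month Visit, item 6c, both arms: "Record any new HbA1c results and changes to medication therapies and/or doses".
- 3-Month Visit: the 3-month arm has the same recording step (item 5.a.iii). For the 6-month arm, item 5b lists only a telephone call: "Contact patient by telephone and ask to perform SMBG four times daily (before all meals and bedtime) for 3 days". No HbA1c recording is listed there.

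**The concern.** Month 6 is the natural time point for the HbA1c comparison, because it is the only post-baseline visit at which HbA1c recording is listed for both arms. A regression of that value on arm alone leaves unused the one measurement most likely to explain variation between patients, and the trial already collects it.

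The change-over-time tests do not fill the gap. Each schedule gets its own test and no arm term is stated, so they appear to describe change within each arm.

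With 9 or 10 evaluable patients per arm, the HbA1c difference will be imprecise and chance differences in baseline HbA1c will be common. The stake is the width of one secondary interval and its exposure to such an imbalance.

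**Working it through.** **The plan's own sample size.** Sample Size and Rationale assumes 60% against 75% of time in range, SD 10 and 90% power. With two-sided 5% assumed, n per arm = 2 × (1.960 + 1.282)² × (10/15)² = 9.3, rounded up to 10, or 20 in total. The stated figure reproduces. It concerns time in range and uses no covariate; there is no HbA1c calculation.

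**Evaluable numbers.** The plan says: "Assuming a 25% drop out, planned enrollment is 25 patients". 25 × 0.75 = 18.75, so 18 whole patients, or 9 per arm. Both 9 and 10 per arm are used below, with 1:1 allocation assumed because the ratio is not stated.

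**Formulas.** The unit is the SD of 6-month HbA1c; r is the baseline to 6-month correlation, which is assumed.

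- Unadjusted: half-width = t(0.975, 2n−2) × √(2/n).
- Adjusted: half-width = t(0.975, 2n−3) × √[(2/n)(1−r²)(1 + 1/(2n−4))]. The last factor allows for expected chance imbalance in the covariate.

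**Worked case, n = 10, r = 0.5.**

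- Unadjusted: 2.101 × √0.2 = 0.940.
- Adjusted: 2.110 × √(0.2 × 0.75 × 1.0625) = 2.110 × 0.399 = 0.842.
- Unadjusted with 12 per arm, for comparison: 2.074 × √(2/12) = 0.847.

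| r | 10 per arm (unadjusted 0.940) | Change | 9 per arm (unadjusted 0.999) | Change |
|---|---|---|---|---|
| 0 | 0.973 | +3.5% | 1.040 | +4.1% |
| 0.2 | 0.953 | +1.4% | 1.019 | +2.0% |
| 0.3 | 0.928 | −1.3% | 0.992 | −0.7% |
| 0.5 | 0.842 | −10.4% | 0.901 | −9.9% |
| 0.7 | 0.695 | −26.1% | 0.743 | −25.7% |

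The two models break even at r = 0.258 (10 per arm) and r = 0.277 (9 per arm).

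**In HbA1c points.** For an assumed SD of 0.7 to 1.25, the half-width at 10 per arm is 0.66 to 1.17 unadjusted (0.940 × SD) and 0.59 to 1.05 at r = 0.5 (0.842 × SD).

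**Difference detectable with 80% power.** At 10 per arm it is 1.325 SD unadjusted, against 1.307, 1.187 and 0.979 SD at r = 0.3, 0.5 and 0.7. At 9 per arm it is 1.407 SD, against 1.395, 1.267 and 1.045 SD.

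**Chance baseline imbalance.** P(|difference| > 0.5 SD) = 2 × [1 − Φ(0.5/√(2/n))] = 0.264 at 10 per arm and 0.289 at 9. At 10 per arm, the mean absolute imbalance in those trials is 0.447 × φ(1.118)/[1 − Φ(1.118)] ≈ 0.724 SD. The unadjusted estimate moves by r times this: 0.217, 0.362 and 0.507 SD at r = 0.3, 0.5 and 0.7. The adjusted estimate moves by 0. Over all randomisations the shift cancels, so it is not bias.

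**Simulation check.** With 100,000 trials per setting and no true arm difference, half-widths (root mean square) agreed with the formulas to 0.001. Type I error was 0.049 to 0.052 for both models.

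**The case against.** The strongest reply is that this is an optimisation, not an error. The unadjusted test holds its type I error, HbA1c is a secondary outcome, and the sample size was never set on it. That stands, and it is why the point is minor.

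A second reply is that silence is not exclusion: a one-paragraph plan names the regressor of interest, and baseline could still be added. That is true. But with about 18 to 20 evaluable patients, leaving the covariate open until the data are seen invites selective reporting.

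Third, the gain depends on a correlation the documents do not give. The entry criterion, "Last 2 HbA1c values between 7.5 – 10% measured in the last 12 months", could lower it by restricting the baseline range, and treatment changes during follow-up could lower it further. This also stands: at 0.3 the gain is close to nil. The trade is still lopsided, with at most 3.5% to 4.1% wider against about 10% narrower at 0.5 and 26% at 0.7.

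Fourth, the outcome might be meant as change from baseline. The text says level. For change at 10 per arm with equal SDs, the half-width is 2.101 × √[0.2 × 2(1−r)], which gives 1.112, 0.940 and 0.728 SD at r = 0.3, 0.5 and 0.7. The adjusted model is narrower each time (0.928, 0.842, 0.695), though at 0.7 the gain is then only about 4.5%.

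Finally, the same sentence names no baseline covariate for time in range, although CGM is worn at baseline in both arms. That is correct, and it does not weaken the HbA1c point.

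**Conclusion.** The concern holds and is minor. The regression is the only stated analysis that compares arms on HbA1c, it names no baseline covariate, and baseline HbA1c is collected from every participant. The planned comparison is valid but probably less precise than it need be: at a correlation of 0.5 the interval is about 10% wider than necessary. Adjustment also guards against a baseline imbalance above 0.5 SD, expected in 26% to 29% of randomisations.

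These sizes assume 1:1 allocation, 9 or 10 evaluable patients per arm, 6-month HbA1c as the outcome and a correlation within the range shown. If the correlation is below about 0.26 to 0.28, adjustment costs a little precision instead.

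**What to change.** In Biostatistics and Data Analysis, state that for Secondary Objective 1 the 6-month HbA1c will be analysed in a linear model with randomised arm and baseline HbA1c as predictors, and that the arm difference will be reported with its 95% confidence interval.

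This changes wording only and needs no new measurement. The model spends one more degree of freedom, so at zero correlation the interval is 3.5% wider with 10 per arm or 4.1% wider with 9. A patient without a 6-month value is missing under either model. A patient without a baseline value would be lost only under the adjusted one, but item 4b already requires that measurement.
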